#### **4.2.2.3. Other Procedural Risks**

Subjects who are pregnant or are breast feeding will be excluded. Subjects who become pregnant during this study will be required to contact their treating physician immediately upon confirmation of the pregnancy.

Routine collection of blood samples requires venipuncture. The risk of simple venipuncture commonly includes discomfort and/or bruising at the site of the puncture, and less commonly, infection at the site of the puncture, the formation of a small blood clot or swelling of the vein and surrounding tissue and bleeding from the puncture site.

These potential other procedural risks are not anticipated to be significantly different than standard of care.

#### **4.2.2.4. Device Related Risks**

Through the Envi™-SR risk assessment process conducted per EN ISO 14971:2012 and

NeuroVasc Technologies, Inc. procedures, a multi-functional team identified risks associated with the design, manufacturing, and use of the device, and identified the characteristics related to its safety. The risks and safety characteristics have been evaluated with respect to the intended users, their level of education and training, and the intended purpose and use of the device.

Risk management and identification was conducted according to EN ISO 14971:2012 and product specific risk analyses, risk management files, and plans. Failure Mode and Effect Analysis (FMEA) was used to identify known risks associated with the development and use of the Envi™-SR and is a “bottoms up” approach to analyzing risk. The technique was applied to three separate categories: 1) the device design, 2) the process, and 3) the user interface. Potential hazards associated with the Envi™-SR were evaluated for their potential effects as well as their potential causes.

Following all mitigations to reduce risk under the risk management process, two (2) risks remained as undesirable:

1. The first is the risk of incorrect patient selection (leading to increased likelihood of futile recanalization or serious adverse events). This hazard is a consequence of the state of the art of stroke treatment based on current imaging and understanding of ischemia. While the rate of good functional outcome (mRS 0-2) has improved markedly with improvements in stroke systems of care and mechanical thrombectomy devices, there still exists significant uncertainty in patient selection. The intended patient population as defined in the NV-001 Study and indications for use of the Envi™-SR are consistent with current therapeutic guidelines and currently cleared Control Devices. This risk is considered reduced as far as possible.
2. The second is the risk that the patient does not receive thrombolytic therapy. Similar to the risk of incorrect patient selection, this hazard relates to state of the art of stroke treatment, and not to mechanical thrombectomy devices. The use of thrombolytic treatment (typically IV t-PA) is a cognizant decision by the treating physician or medical team, not a “user error” based on the patient. The use of t-PA in the NV-001 Study follows established indications for use in the US and is considered reduced as far as possible.

As with all mechanical thrombectomy procedures, there is a possibility that serious Adverse Events may occur. Treatment with the Envi™-SR device may have unanticipated effects that no one knows about yet. In addition, risks due to subjects’ individual reaction to the Envi™-SR device or its components, or to the control device could occur. Should any Adverse Events occur, they will be fully examined and monitored closely with special attention to UADEs as described in Section 12.

### **4.2.3. Risk Mitigation**

#### **4.2.3.1. Study/Procedure Related Risk Mitigation**

Participating study sites will be assessed to ensure that the requirements and controls necessary for this trial are met prior to screening and enrolling subjects. Refer to Section 6.4 for these criteria.

Each subject or LAR will be required to review and sign an Informed Consent Form (ICF) prior to participation, see Section 5.2. The ICF will explain the intent and design of the trial, alternative treatment methods as well as the risks and potential benefits of participation.

An adaptive trial design is employed to limit study risk by stopping the trial for futility or early demonstration of non-inferiority. Stopping rules have been pre-specified.

Independent oversight via the DMC, CEC, and Core Lab ensures that risks to participating subjects will be minimized. Safety monitoring of the data, consisting of individual event and aggregate data review, will be ongoing and conducted at a rate commensurate with subject enrollment in the trial. Specifically, the DMC will monitor adverse events and their occurrence rate throughout the study to advise on study continuation, modification or adjournment based on a review of a review of the comparative rates of Adverse Events of Special Interest. They will take into account in their decision making and recommendations the rates of procedure-related and device-related events in the control and treatment arms, refer to Section 12.3.

#### **4.2.3.2. Device Related Risks Mitigation**

Risk mitigation activities were conducted according to EN ISO 14971:2012 and product specific risk analyses, risk management files, and plans. Design, Process, and Use FMEAs identified hazards associated with the Envi™-SR design, manufacturing, and usage. Hazards were evaluated for potential hazardous situations, which were in turn evaluated for the potential to cause harm(s). The severity, likelihood, and detection (if applicable) of each risk sequence was evaluated for potential mitigation. Mitigations were implemented to reduce risk, and all risks identified were mitigated as far as possible. Residual risk levels have been deemed acceptable and appropriate for the intended use of the device.

The Envi™-SR is designed and manufactured in such a way that, when used under the conditions and for the purposes intended, it is not anticipated to compromise the clinical condition or the safety of patients or users. The risk management process has identified and reduced risks including user error as far as possible.

The risks and safety characteristics have been evaluated with respect to the intended users, their level of education and training, and the intended purpose and use of the device. Use risk will be minimized by selecting investigators experienced and skilled in mechanical thrombectomy and who have been trained in the NV-001 Study protocol per Section 13.

#### **4.2.4. Assessment of Potential Benefits of the Proposed Investigation**

The benefit of mechanical thrombectomy with stent retrievers is well established and has led to their adoption as the standard of care for a subset of patients experiencing AIS due to LVO in select patients up to 24 hours after stroke onset.

The Envi™-SR method of action is similar to other mechanical thrombectomy retrievers currently available in the US, Europe and other regions around the world, including the Control Devices. In contrast to other retrievers, the Envi™-SR is designed with eccentrically mounted articulating segments. Testing with the Envi™ System retriever component in an *in vitro* model showed enhanced clot retrieval versus non-segmental designs when retrieved in tortuosity. The Envi™ System retriever also underwent a First-in-human trial in Japan. The Envi™-SR was based on the Envi™ System retriever component optimized for usage as the sole thrombectomy device. In pre-clinical testing in swine, the Envi™-SR demonstrated non-inferiority in various safety and effectiveness endpoints. Based on the similarity in method of action, *in vitro* and *in vivo* pre-clinical testing, clinical evaluation, and early clinical experience, the Envi™-SR is expected to be non-inferior to currently available stent retrievers.

Clinical effectiveness of the Envi™-SR has not been established and acute and long-term benefit to subjects that volunteer for enrollment in this trial are unknown.

#### **4.2.5. Consideration of Patient Preference Information**

The Envi™-SR and Control Devices are prescription-only devices used in emergency procedures and are not expected to have significant patient preference considerations.

#### **4.2.6. Assessment of Uncertainty**

As the benefit of mechanical thrombectomy with stent retrievers in the treatment of AIS has been well established, the uncertainty of benefit and risk of this trial is predominantly regarding the Envi™-SR device. In the absence of a pivotal clinical trial, the safety and effectiveness of the Envi™-SR is uncertain, and subjects may receive no direct benefit from study participation.

Non-clinical bench testing has consistently demonstrated the ability of the Envi™-SR and the previous generation Envi™ System retriever to meet product specifications and user needs. These data have supported the CE mark of the Envi™-SR and the previous generation Envi™ System retriever. Pre-clinical GLP animal data is consistent with bench testing data and supports the acceptability of risks and potential benefits.

Limited clinical experience on the Envi™ (aka Versi) Retriever in Japan and Europe has provided additional validation in humans supporting the acceptability of the risk profile, which reduces the uncertainty of risks and potential benefit. Limited commercial experience with the Envi™-SR has provided no indication of unanticipated risks and further reduces uncertainty. This study is designed as a prospective, multinational, randomized, parallel group-controlled, blinded, non-inferiority study in order to reduce uncertainty and establish the safety and effectiveness of the Envi™-SR.

#### **4.2.7. Risk Benefit Conclusion**

The undesirable residual risks noted are related to the state of the art of stroke treatment and not to the Envi™-SR specifically, and have been mitigated as far as possible in the NV-001 Study. The benefits of mechanical thrombectomy with the Control Devices have been demonstrated by multiple prospective randomized trials to outweigh the risks of treatment in the indicated patient population. The Envi™-SR is expected to provide a similar benefit / risk profile.

The Envi™-SR may offer benefits in revascularization when retrieved in neurovascular tortuosity, which may be predictive of better clinical outcomes. Despite inherent risks in treating patients who present with AIS, available information indicates the Envi™-SR has a risk/benefit profile not inferior to cleared devices, and when monitored and conducted per the protocol the potential benefits of treatment with the Envi™-SR justifies the risks.

## **5. Subject Selection**

### **5.1. Enrollment**

#### **5.1.1. Enrolled Population**

All consecutive patients with a signed Informed Consent Form (ICF) will be considered part of the enrolled population.

##### **5.1.1.1. Enrolled Screen Failures**

Subjects who are consented but do not meet all inclusion/exclusion criteria, are not randomized and device placement is not attempted, will be classified as enrolled screen failures. All patients that are consented are enrolled subjects and will count toward the total allowed study enrollment even if they are determined to be screen failures after consent.

#### **5.1.2. Intention to Treat (ITT) Population**

A subject that is enrolled and randomized to a treatment arm is considered part of the ITT population. The ITT population will form the basis for the primary analysis dataset, independent of the subject actually receiving the randomized device.

#### **5.1.3. Per Protocol Population**

An enrolled subject that meets all inclusion/exclusion criteria, receives the randomized device, and has no major protocol deviations that significantly change the intent or outcome of the protocol for the subject will be considered part of the Per Protocol (PP) population.

#### **5.1.4. As-Treated Population**

An enrolled subject that receives treatment with either the Envi™-SR or a Control Device after consent and randomization will be analyzed according to the treatment received (regardless of randomization) in the As-Treated population analysis.

### **5.2. Informed Consent**

Prior to admission to the study, a patient Informed Consent Form (ICF) will be given to each prospective subject or their LAR (as defined by the local IRB/EC/REB), including an explanation of the study, duration, explanation of medical record access and patient anonymity, and how their coded data may be transferred, used for publications or in submissions for reimbursement support. The ICF will contain language that is non-technical and understandable (translated ICFs will be provided where applicable) to the patient or his/her legal representative. The treatment occurs in an acute emergency situation, so locally required ICF procedures may apply and will be complied with.

Each potential subject will be provided with written and verbal information regarding the nature of the study in an understandable manner. Adequate time will be allowed for the subject to consider participation in the clinical study. Signed, written consent will be obtained for each subject prior to data collection and entry into the study. Any coercion or undue influence of potential subjects to participate must be avoided, and the subject's legal rights should not be waived. The Investigator or an appropriately designated member of the study staff shall co-sign the consent form, indicating they believe the subject has understood the nature and risks of the study and, in their estimation, the subject clearly understands the scope of the consent. The Investigator must inform subjects that they are in a controlled clinical study, apprise them of their rights as set forth in the ICF, and document the discussion in their medical record.

If the subject is not able to give his/her informed consent to participate in the study, a LAR can sign the ICF for the subject if this is approved by the IRB/EC/REB.

Short form informed consent, electronic consent, or appropriate teleconsent platforms may be utilized if approved by the IRB/EC/REB. Each institution must follow their institutional IRB/EC/REB policy for obtaining informed consent. If the short form, or alternative (e.g., teleconsent) informed consent is used, the summary must include all the basic elements of informed consent (21 CFR 50.25; ICH E6 4.8.10).

The procedure around how the informed consent is collected will be recorded in each subjects' medical record. The signed ICFs will be retained by the Investigators and made available (for review only) to the study monitor/auditor on request.

Each site will maintain a log of all screened patients detailing the reasons for any subsequent patient exclusions or non-participation in the study.

### **5.3. Subject Withdrawals**

Participation in this IDE Study is voluntary, and the subject may withdraw at any time. All ITT subjects will be included in data analysis, unless they withdraw permission for their data to be used. The Sponsor will retain and continue to use any data collected prior to the withdrawal of informed consent, unless specified by the subject or their LAR.

In the event the subject chooses to withdraw, he/she will be instructed to contact the Investigator immediately. Withdrawal from the investigation will not affect the subject's follow-up care. The subject will be informed of any significant information regarding new findings that may develop during the course of the research study that may relate to his or her willingness to continue participation as a study subject.

Subjects will participate in their routine follow-up and allow this data to be gathered or their participation in the study will be prematurely terminated. If their participation is terminated, any of their data which has been already gathered will continue to be included. The completion of a subject's participation in the study or early departure from the study must be fully documented in the subject's study progress notes.

Subjects will be considered exited (i.e., discontinued) from the study if any of the following occur:

1. If, during the conduct of the study, a subject dies, all available information should be obtained, and an appointed NeuroVasc Technologies representative/ study monitor should be notified no more than 24 hours from study staff becoming aware of the event.
  - a. If a subject's death occurs while in the hospital, submit a copy of the physician's death summary report. If an autopsy is performed, submit a copy of the autopsy report, as well. If a subject's death occurs outside of the study site, obtain all information related to the death and submit the investigator's summary of the events associated with the death.
2. Subject voluntarily withdraws from the study. A subject may withdraw consent from study participation at any time.
3. Subject does not meet inclusion / exclusion criteria after consent but prior to randomization (enrolled screen failure). The subject will be followed for a minimum of 48 hours or until discharge, whichever is earlier, and exited from the study.
4. Subject withdrawn from the study by the investigator. An investigator may withdraw an enrolled subject from the study for the following reasons:

a. Major Protocol Deviation:

Should a subject be enrolled but later determined ineligible based on previously unavailable source documentation or due to a deviation in following the protocol at the study site, this subject will be considered a major protocol deviation. A comparison of the incidence of patients who have a major protocol deviation will be performed between the randomized treatment groups. A 2-tailed Fisher's exact test will be used to determine if the proportion of patients with deviations differs significantly between the 2 treatments.

All protocol deviations should be documented by the study monitor appointed by NeuroVasc Technologies.

b. Subject is Lost to Follow-up

c. Investigator's discretion

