### 3.6. Blinding

Each participating clinical site will have two (2) teams: an **unblinded team**, consisting of treating physicians and study coordinator who care for the patient/patient up to hospital discharge and clinical follow up visits, and a **blinded team**, with members certified in mRS assessment. The blinded team performs the mRS assessment at the 90-day visit, and the NIHSS assessment at the 24-hour and 7-day/discharge visits.

The Investigator will be blinded to treatment arm during screening, consent and enrollment, until point of randomization. At the point of randomization, the Investigator will be informed of which device is to be used in the procedure in order to safely perform the procedure according to the device IFU.

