#### **6.8.2.8. Screen Failure After Randomization – Follow-up**

Subjects that have been enrolled and randomized but subsequently are found to not meet inclusion / exclusion criteria will be recorded in the Deviation eCRF as a protocol deviation. These subjects are a part of the ITT population regardless of treatment and will be followed per standard study procedures.

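### Section 5.3 lets an unblinded investigator exit a randomised subject before day 90, so an obtainable 90-day mRS is imputed instead of collected; its ineligibility ground also contradicts section 6.8.2.8

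*Combined protocol and SAP*

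**What the plan says.** Protocol section 5.3 (Subject Withdrawals) lists the ways in which a subject is considered exited. Item 3 deals with screen failure between consent and randomisation. Item 4 is separate: "An investigator may withdraw an enrolled subject from the study for the following reasons". Its grounds are:

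- 4a, a major protocol deviation, described as: "Should a subject be enrolled but later determined ineligible based on previously unavailable source documentation or due to a deviation in following the protocol";
- 4b, loss to follow-up;
- 4c, given in full as "c. Investigator's discretion".

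Enrolment means consent. Section 5.1.1 states: "All consecutive patients with a signed Informed Consent Form (ICF) will be considered part of the enrolled population". A randomised subject is therefore still an enrolled subject.

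On blinding, section 3.6 states: "At the point of randomization, the Investigator will be informed of which device is to be used in the procedure".

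On data, section 5.3 keeps all ITT subjects in the analysis unless they withdraw permission for use of their data. For a subject whose participation is terminated, it adds that "any of their data which has been already gathered will continue to be included".

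Section 6.8.2.8 covers subjects found after randomisation not to meet the entry criteria: "These subjects are a part of the ITT population regardless of treatment and will be followed per standard study procedures".

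Section 8.2.2 applies multiple imputation to subjects who withdraw prematurely. The variables listed are age, occlusion site, baseline NIHSS, prior IV t-PA, time to symptom onset and baseline ASPECTS.

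**The concern.** A person who knows the arm and has seen the angiographic result may end a randomised subject's participation before the primary outcome is due. One of the grounds has no criteria. The subject stays in the ITT set, but the ITT label does not supply a 90-day mRS that nobody collected.

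The imputation list holds baseline factors only. It includes neither the procedural result nor the 30-day mRS that section 6.8.6 schedules. A subject exited after a poor procedure would be imputed like any other subject with the same baseline profile. If such exits were more common in one arm, the estimated difference would shift towards that arm. In a non-inferiority trial, a shift towards Envi-SR raises the chance of a false claim.

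There is also a plain inconsistency. Two sites that both follow the protocol could treat the same ineligible randomised subject differently: one exits the subject under 4a, the other follows the subject to day 90 under 6.8.2.8.

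**Working it through.** **1. Does item 4 reach randomised subjects?** Yes. Enrolled means consented (5.1.1), and item 3 already takes the period before randomisation. Ground 4a itself calls for a comparison of deviations between the randomised groups.

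**2. Where is the contradiction?**

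| Situation after randomisation | Section 5.3 | Section 6.8.2.8 |
|---|---|---|
| Found ineligible | May be exited (4a) | Stays in ITT, followed as standard |
| Other deviation | May be exited (4a, on one reading) | Silent |
| Investigator's discretion | May be exited (4c) | Silent |

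Only the first row is a direct contradiction. The other two are an unrestricted permission held by an unblinded person.

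**3. The plan's own figures.** Inputs are a margin of 12.5 points, one-sided alpha 0.025, 80% power and 1:1 allocation. The Farrington–Manning score formula gives 270 for 46% against 50.5%, and 426 for 49.5% against 50.5%. Then 426 × 1.05 = 447.3, rounded up to 448. All three agree with section 8.2. (The power behind the 270 is not stated; 80% is taken from the maximum-sample-size paragraph.)

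**4. Size of a possible bias (illustration).** Assumptions: the true difference lies at the margin (Control 46%, Envi-SR 33.5%); 5% of the Envi-SR arm is withdrawn and none informatively in Control; true success among those withdrawn is 20 to 30 points below the imputed rate. The documents give neither a withdrawal rate nor a gap.

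- Bias = share withdrawn × (imputed rate − true rate): 0.05 × 0.20 = 0.010 and 0.05 × 0.30 = 0.015.
- SE = √[(0.46×0.54 + 0.335×0.665)/n per arm] = √(0.4712/135) = 0.0591, or √(0.4712/224) = 0.0459.
- Type I error = P(Z > 1.96 − bias/SE).

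| Total N | Bias | 1.96 − bias/SE | Type I error |
|---|---|---|---|
| 270 | +1.0 points | 1.791 | 3.7% |
| 270 | +1.5 points | 1.706 | 4.4% |
| 448 | +1.0 points | 1.742 | 4.1% |
| 448 | +1.5 points | 1.633 | 5.1% |

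Five per cent of an arm is about 7 subjects (0.05 × 135 = 6.75) or 11 (0.05 × 224 = 11.2).

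**5. Cases without net bias.** With the same share and gap in both arms, for example 25 points, the net bias is 0.05 × 0.25 − 0.05 × 0.25 = 0. If informative withdrawal is heavier in Control, the sign reverses. If withdrawal is unrelated to outcome and imputation is arm-specific, there is no bias. The cost at 5% is then about two points of power: 79.9% to 77.9% at 135 per arm, and 81.5% to 79.5% at 224 per arm.

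**6. Do the planned analyses recover the outcomes?**

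- Fisher's exact test on deviations (5.3) can show an imbalance but returns no mRS.
- Carrying the last post-procedure observation forward (8.2.2) needs such an observation. The first scheduled post-procedure mRS is at 30 days, so an earlier exit usually leaves none.
- Baseline imputation (8.3.1) uses the pre-stroke mRS, which must be 2 or less, so every eligible subject counts as a success. Worst-score imputation works in the other direction. Section 8.3.1 words both for subjects lost to follow-up.
- The tipping-point analysis (8.2.2) shows how fragile the result is, but does not supply the missing values.

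**The case against.** The strongest reply has four parts.

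*Recorded data are safe.* This stands. A reader might infer from 5.3 that an investigator can remove a 90-day mRS already in hand. The documents do not support that, because data gathered before exit remain in the analysis. What is lost is an outcome not yet collected.

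*Ground 4a is only a classification, and perhaps only about ineligibility.* The wording "due to a deviation in following the protocol at the study site, this subject will be considered a major protocol deviation" labels the subject rather than ordering an exit, and item 4 is permissive. The sentence can also be read so that the deviation is merely a cause of ineligibility. On that reading, early additional therapy or use of the wrong device is no ground for exit; elsewhere, early additional therapy without a valid exception leads to exclusion from the per-protocol set (3.5). This stands as a possible reading. But 4a is listed as a reason for withdrawal, and section 9 sets continuing in the study against being considered a major deviation as alternatives. Ground 4c remains open on any reading.

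*The conflict with 6.8.2.8 is narrow.* This stands too. A reader might take the whole of item 4 to contradict 6.8.2.8. That section speaks only of ineligibility found after randomisation.

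*The error rates are hypothetical, and safeguards exist.* The one-arm scenario is an assumption, and a reader should not infer that inflation above 2.5% is expected. The sensitivity analyses, and the DMC's monitoring of retention (12.3), may reveal a problem. They do not repair the primary estimate. The protocol refers to the SAP for the code that handles missing mRS. That code is not in the text available for this check, so a fuller imputation model there cannot be ruled out.

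**Conclusion.** The point holds in a limited form. Two findings need no numerical assumption. First, section 5.3 lets an investigator who knows the arm end follow-up of a randomised subject, with no criteria for discretion. Second, its ineligibility ground contradicts 6.8.2.8. The consequence is avoidable missing primary outcome data, imputed from baseline factors if the list in 8.2.2 is complete.

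The numerical effect is an illustration: +1.0 to +1.5 points of bias, with type I error of 3.7–4.4% at N=270 or 4.1–5.1% at N=448. It depends on 5% informative withdrawal in the Envi-SR arm alone and a gap of 20 to 30 points. It vanishes when withdrawal and gaps are equal in both arms, and its direction is not known in advance. The change should be made because it removes an avoidable risk to the primary estimate; no bias has been shown.

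**What to change.** In section 5.3, either limit grounds 4a and 4c to subjects not yet randomised, or state that after randomisation a deviation, ineligibility or investigator decision does not end follow-up. Require the blinded 90-day mRS and vital status for every randomised subject. The only exceptions should be withdrawal of consent, death (scored mRS 6, as in Appendix A) and loss to follow-up after the steps in section 5.4. Add a cross-reference to 6.8.2.8 so that the two sections agree, and report any investigator withdrawal by arm and reason.

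The cost is a protocol wording change. The 90-day visit is already planned for every ITT subject, and the required sample sizes of 270 and 426 do not change.
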